7.6 Interim analysis

No interim analysis is planned.

7.7 Data Monitoring Committee

No Data Monitoring Committee has been established.

7.8 Handling of missing and incomplete data

All reasonable efforts will be made to reduce the rate of missing data. Investigators will be trained about the importance of patient retention and full data capture. Also, any reasonable attempts should be made by the investigators to emphasize continued subject's participation for the full duration of the trial.

Patients who discontinue the treatment will not be withdrawn from the study by default but will be asked to complete safety and efficacy observations as per the protocol, unless otherwise they withdraw their consent. Patients who discontinue study treatment and decide to remain in the study by following the schedule of assessments and continuing to adhere to protocol requirements are defined as “retrieved drop-out” patients.

For the primary and key secondary analyses, missing data will be handled by means of Multiple Imputation using retrieve dropouts (MI-RD), as detailed in sections 10.1.2 and 10.2.2.

In addition, to further minimize missing data, if a patient cannot refer to the site for a planned follow-up visit, the investigator will try to obtain any relevant information from the patients, including documents/laboratory results available from local medical care.

The number of subjects with missing data will be presented under the “Missing” category. Missing values will not be included in the denominator count when computing percentages. When continuous data will be summarized, only the non-missing values will be evaluated for computing summary statistics.

For the analyses of parameters for which an independent blinded reading center may be involved per protocol, the following rules will be used:

1. If assessment from blinded reading center is available, such value will be used for the analysis.
2. If assessment from blinded reading center is not available, the corresponding evaluation (if any) from the site investigator will be used.
3. If both assessments (blinded reading center and site investigator) are not available, a statistical imputation method will be applied as described in this SAP.

Rules for handling missing data of IDEEL questionnaire are reported in section 12.3, according to the dedicated manual.

7.9 Changes in the planned analysis

The following changes have been included, compared to the protocol [1]:

- In the secondary endpoint on SANDE, the global score has been included (section 3.2.2) in addition to severity and frequency scores.
- In the explorative endpoint on SANDE, the global score has been included (section 3.2.3) in addition to severity and frequency scores.
- A clarification on the use of data from blinded reading center and site investigator has been added in section 7.8.
- The first key secondary endpoint in section 10.2.1 has been reworded in alignment with the definition of the Schirmer I test primary endpoint.
- A clarification on the use of a Mixed Model for Repeated Measurements (MMRM), extension of ANCOVA for repeated measurements, after imputation through MI-RD for IDEEL, NEI scale and TFBUT endpoints has been added in section 10.2.2, in alignment with treatment policy estimand used for primary endpoint.
- Considering the progress of data collection, the overview of planned statistical analyses (section 6.2) has been updated. A single database lock will be performed at the end of the study (instead of two locks), followed by the release of the KFR and by the final analyses. This decision represents a conservative choice in favor of the integrity of the study.

7.10 Blind Data Review Meeting (BDRM)

BDRMs will be held before DB locks. Any other details will be provided in the BDRM documentation (Pre-Analysis Review).

7.11 Software

All statistical analyses and data processing will be performed using Statistical Analysis Systems (SAS®) Software (release 9.4 or later).

8. Evaluation of Demographic and Baseline Characteristics

8.1 Subject enrolment and disposition

All presentations of subject disposition will be by treatment group, and overall.

For describing the subject disposition, the following populations will be summarized:

1. Subjects screened overall (N).
2. Subjects enrolled overall (N, 100%).
3. Subjects enrolled but not randomized and reasons for non-allocation overall (N, %).
4. Subjects randomized by treatment group, and overall (N, %).
5. Subjects randomized but not treated by treatment group, and overall (N, %).
6. Subjects in each analysis set (FAS, SAF, PP) and reasons for exclusion by treatment group, and overall (N, %).

For points 1 - 3, the percentage denominator will be the number of ENR subjects; for points 4 - 6, the percentage denominator will be the number of randomized subjects within each arm.

Listings will be provided based on ENR set.

8.2 Protocol deviations

All the protocol deviations will be discussed case by case before unblinding of the treatment code with the clinical team during the BDRM and described in the BDRM Report. Any deviation from these protocol procedures will be reported in the study-specific Protocol Deviation form.

Number of occurrences and of subjects with at least one major and minor protocol deviation will be summarized for each treatment and overall.

8.3 Study discontinuations

The following information will be summarized for the randomized patients by treatment and overall:

- Trial completers.
- Subjects who discontinued the trial prematurely (and reasons).
- Number of subjects who completed each planned visit.

- Subjects who discontinued the IMP (and reasons).
- Subjects who discontinued the IMP but completed the study.
- Subjects who discontinued the IMP and discontinued the trial prematurely.
- Broken randomization code (and reasons).

If more than 30% of randomized subjects discontinue the study prematurely, the distribution of the time from randomization to discontinuation will be summarized using the Kaplan-Meier method. The degree of uncertainty will be expressed with 95% confidence limits (calculated per the method proposed by Greenwood). Comparison of curves among arms will be performed with the log-rank test. Kaplan-Meier graphs will be presented along with the number of patient-at-risk at exact time points. Subjects who have not prematurely discontinued the trial will be censored at study termination.

8.4 Demographics and baseline characteristics

The baseline demographic characteristics will be summarized by treatment and overall, by means of descriptive statistics. No statistical testing will be carried out.

The following demographic and baseline characteristics will be reported:

- Geographic region of the site (EU, US) ,
- Site,
- Age (years),
- Sex (Male, Female),
- Race,
- Ethnicity,
- Potential childbearing
- Contraception method
- Pregnancy test performed and result and reasons for no pregnancy test.

8.5 Ocular and systemic Medical History and Concomitant Diseases

A disease is defined:

- “Previous disease” if it is not ongoing at screening visit (“ongoing” box is ticked as “No”).
- “Concomitant disease” if it is ongoing at screening visit (“ongoing” box is ticked as “Yes”).

Previous and/or concomitant diseases will be coded using Medical Dictionary for regulatory activities (MedDRA) dictionary and reported in separate tabulations. Frequency distributions and percentages will be summarized by treatment, type (Ophthalmic and Non-Ophthalmic), by System Organ Class (SOC) and Preferred Term (PT).

Counts will be given for both SOC and PT by subject. Subjects experiencing more than one previous/concomitant disease event will be counted only once within each SOC and PT.

Subjects experiencing more than one disease classified in the same category will be counted only once.

8.6 Prior and concomitant medications

A medication is defined:

- “Prior medication” if taken and stopped prior to first dose of study treatment.
- “Concomitant medication” if taken after the first dose of study treatment.

according to the available parts of the medication dates (see Table 7). In case of missing information not directly allowing allocation to either of the two above categories of medications, the medication will be considered as concomitant.

Prior and/or concomitant medications will be coded using World Health Organization Drug Dictionary and reported in separate tabulations. Frequency distributions and percentages will be summarized by treatment, type (Ophthalmic and Non-Ophthalmic), by Anatomical Main Group (1st level of the Anatomical Therapeutic Chemical (ATC) classification), Chemical Subgroup (4th level of the ATC classification) and Preferred Name.

Subjects taking more than one medication classified in the same category will be counted only once.

8.7 Dry Eye History

The dry eye history characteristics will be summarized by treatment and overall, by means of descriptive statistics. No statistical testing will be carried out. The following information will be reported:

- Eye affected by Dry Eye.
- Time since first diagnosis of Dry Eye.
- Has the patient received prior treatment for dry eye?
- Eye diagnosed with Severe Sjögren's Dry Eye.
- Time since first diagnosis of Severe Sjögren's Dry Eye.

8.8 Other baseline characteristics

No statistical testing will be carried out for comparing baseline characteristics.

8.8.1 Eligible eye

Eye which is defined as eligible eye and the used criteria (IE, Worst Schirmer's test, Worst NEI score, investigator's judgement, right as per protocol rule) will be reported.

8.8.2 SANDE

Baseline SANDE scores (frequency, severity, and overall) will be descriptively summarized by treatment and overall as a continuous variable. Information on the SANDE assessment (done/not done) will be reported, with reasons in case of not execution. Rules for derivation of SANDE scores are reported in section 12.2.

8.8.3 IDEEL

Baseline IDEEL scores will be descriptively summarized by treatment and overall as a continuous variable. Information on the IDEEL assessment (done/not done) will be reported, with reasons in case of not execution. Rules for derivation of IDEEL scores are reported in section 12.3.

8.8.4 BCDVA

Baseline SNELLEN equivalent scores will be summarized by treatment and overall as an ordinal variable for the right eye, the left eye and eligible eye. Information on the BCDVA assessment (done/not done) will be reported, with reasons in case of not execution.

8.8.5 External ocular examination

The results of the external ocular examination will be summarized by treatment and overall, by means of descriptive statistics. Information on the assessment (done/not done) will be reported, with reasons in case of not execution. The following information will be reported for the eligible eye:

- Any clinically significant abnormalities and types.
- Any evidence of punctual occlusion.
 - if yes, by what mechanism was this seen.
- Any clinically significant abnormalities in the function of the eyelid muscles.
 - if yes, specification.
- Any abnormalities in the conjunctiva and types.

The same information will be provided, in a separate tabulation, for the non-eligible eye.

8.8.6 Schirmer test I and Schirmer test II

Baseline Schirmer test I and Schirmer test II will be descriptively summarized by treatment and overall as continuous variables. Information on the assessments (done/not done) will be reported, with reasons in case of not execution.

8.8.7 Slit Lamp Ophthalmic Exam

The results of the Slit Lamp Ophthalmic Exam will be summarized by treatment and overall, by means of descriptive statistics. Information on the assessment (done/not done) will be reported, with reasons in case of not execution. The following information will be reported for the eligible eye:

- Evaluation.
 - if Abnormal, comments.
- Horizontal diameter of the cornea (mm).

8.8.8 Fluorescein Staining (NEI Scale)

The results of the Fluorescein Staining will be summarized by treatment and overall, by means of descriptive statistics. Information on the assessment (done/not done) will be reported, with reasons in case of not execution. The following information will be reported for the eligible eye:

- Has Ocular surface staining performed?
- Cornea – Result.
- Conjunctiva – Result.
- Total Cornea Score.
- Total Conjunctiva Score.

Rules for derivation of NEI scores are reported in section 12.4.

8.8.9 Tear Film Break-up Time (TFBUT)

Baseline TFBUT results will be summarized by treatment and overall as a continuous variable for the right eye, the left eye and eligible eye. Information on the TFBUT assessment (done/not done) will be reported, with reasons in case of not execution.

9. Evaluation of Treatment Compliance and Exposure

9.1 Compliance to IMP

The assessment of patients' compliance to the IMP will be made by determining the number of drops administered to the eligible eye. On a per patient basis, the evaluation of the compliance will be done using the following formula:

$$\text{Compliance (\%)} = \frac{\text{total number of drops in the eligible eye taken during the treatment period}}{\text{total number of drops in the eligible eye scheduled during the treatment period}} \times 100$$

Where derivations rules for “*total number of drops in the eligible eye taken during the treatment period*” and for “*total number of drops in the eligible eye scheduled during the treatment period*” are provided in Table 3.

Compliance will be summarized by treatment and overall, by means of summary statistics. In addition, compliance to IMP will also be presented for the following categories: <80%, 80%-120%, >120%.

9.2 Exposure to IMP

The extent of exposure to IMP in days will be summarized with descriptive statistics by treatment group and overall. The extent of exposure (days) will be calculated using the formula reported in Table 3.

9.3 Use of preservative free artificial tears

The use (n° drops/day) of preservative free artificial tears will be summarized with descriptive statistics by treatment group and overall, by study period (treatment / follow-up) and overall according to the following formulas:

$$\text{Use}_{TREAT} = \frac{\text{total number of drops of the preservative free artificial tears during the treatment period}}{\text{total number of days of the treatment period}} \times 100$$

$$\text{Use}_{F-UP} = \frac{\text{total number of drops of the preservative free artificial tears during the follow-up period}}{\text{total number of days of the follow-up period}} \times 100$$

Details are provided in Table 3.

10. Evaluation of Efficacy

10.1 Analysis of primary efficacy endpoint

10.1.1 Testing strategy and multiplicity adjustment

The following null hypothesis is defined on the first primary endpoint: the proportion of patients reaching a value of Schirmer I test (without anesthesia) $>10\text{mm}/5\text{min}$ at week 4 in cenegegermin (rhNGF) is lower or equal than control:

$$H_{01}: T_{\text{rhNGF}} \leq T_{\text{CONTROL}}$$

$$H_{11}: T_{\text{rhNGF}} > T_{\text{CONTROL}}$$

where T_{rhNGF} and T_{CONTROL} are the proportion of patients reaching a value of Schirmer I test (without anesthesia) $>10\text{mm}/5\text{min}$ at week 4 for cenegegermin and control groups, respectively. The null hypothesis H_{01} will be rejected if the associated primary analysis p-value will be lower than 0.025.

Similarly, the following null hypothesis is defined on the co-primary endpoint: the change from baseline (reduction) in the global SANDE score at week 12 in cenegegermin is lower or equal than control:

$$H_{02}: \mu_{\text{rhNGF}} \leq \mu_{\text{CONTROL}}$$

$$H_{12}: \mu_{\text{rhNGF}} > \mu_{\text{CONTROL}}$$

where μ_{rhNGF} and μ_{CONTROL} are the change from baseline (reduction) in the global SANDE score at week 12 for cenegegermin and control groups, respectively. The null hypothesis H_{02} will be rejected if the associated primary analysis p-value will be lower than 0.025.

Both null hypotheses H_{01} and H_{02} must be rejected to claim superiority of cenegegermin over control. Consequently, no multiplicity correction of type I error will be applied on primary endpoints analysis.

10.1.2 Analysis details

Both co-primary endpoints will be analysed by means of MI-RD to handle missing data. Retrieved drop-out patients are defined as patients who discontinue study treatment and decide to remain in the study by following the schedule of assessments and continuing to adhere to protocol requirements. Consequently, for each primary endpoint, MI will be performed based on the subjects' allocated treatment arm and observed values (baseline and intermediate) as covariates in a regression model using data from Retrieved drop-out patients that have the primary endpoint assessment done.

10.1.2.1 Schirmer I test $>10\text{mm}/5\text{min}$ at week 4

This primary endpoint will be analyzed by means of a logistic regression model adjusting by pre-defined baseline factors (gender, age class, baseline Schirmer I test value as fixed effects and site as random effect) and a one-sided test will be used to test for differences between treatment groups.

For the imputation of missing data of Schirmer I test, a regression model will be created by including the baseline Schirmer I test value, gender, age class, and Schirmer I test at week 2. Two hundred data sets will be generated, and the random seed number will be 820520. MI will be implemented in the following steps:

1. Partial imputation assuming Missing at Random (MAR) will be carried out to impute intermittent (non-monotone) missing data of Schirmer I test up to week 4 based on a

multivariate joint Gaussian imputation model using the Markov chain Monte Carlo (MCMC) method. A separate imputation model will be used for each treatment arm. In case of non-convergence or non-estimability issues, a single imputation model will be considered (with treatment arm added as explanatory variable to the model). A total of 200 datasets will be created. These datasets will be utilized in Step #2.

2. The remaining monotone missing data will be imputed using a MI regression including the same explanatory variables of the previous step. According to MI-RD approach, only non-missing values from retrieve dropouts will be used to inform the regression model.
3. Each of the 200 imputed datasets will be analyzed using observed and imputed data. Rubin's rule will be used for combining results to draw inference.

If there are not enough retrieved dropouts for convergence of MI-RD regression model, a reference-based Multiple Imputation (MI) approach will be adopted to consider a missing not at random (MNAR) mechanism for missing data: imputation of values in the rhNGF arm (above step #2) will be done using the non-missing values from the control group (this approach will be referred as "Copy Reference"). This approach does not assume benefits for rhNGF in case of discontinuation and limits a post-discontinuation clinical effect to that of vehicle. The final decision on the use of the MI-RD vs Copy-Reference for this endpoint will be done at the time of the analysis and reported in the CSR.

Whether for MI-RD or Copy-Reference approach, the adjusted estimated treatment differences in proportions between cenegegermin and vehicle at week 4 will be displayed together with the corresponding two-side 95% confidence intervals and p-value.

10.1.2.2 Change from baseline in the global SANDE score at week 12

This co-primary endpoint will be analyzed by means of an Analysis of Covariance (ANCOVA) adjusting by pre-defined baseline factors (gender, age class, baseline global SANDE score as fixed effects and site as random effect) and a one-sided test will be used to test for differences between treatment groups. Rules for derivation of SANDE scores are reported in section 12.2.

For the imputation of missing data, a regression model will be created by including the baseline global SANDE score, gender, age class, and intermediate global SANDE scores up to week 12. Two hundred data sets will be generated, and the random seed number will be 37103939. MI will be implemented in the following steps:

1. Partial imputation assuming MAR will be carried out to impute intermittent (non-monotone) missing data of global SANDE score based on a multivariate joint Gaussian imputation model using the MCMC method. A separate imputation model will be used for each treatment arm. In case of non-convergence or non-estimability issues, a single imputation model will be considered (with treatment arm added as explanatory variable to the model). A total of 200 datasets will be created. These datasets will be utilized in Step #2.
2. The remaining monotone missing data will be imputed using a MI regression including the same explanatory variables of the previous step. According to MI-RD approach, only non-missing values from retrieve dropouts will be used to inform the regression model.
3. Each of the 200 imputed datasets will be analyzed using observed and imputed data. Rubin's rule will be used for combining results to draw inference.

If there are not enough retrieved dropouts for convergence of MI-RD regression model, a Copy Reference approach will be adopted to consider a MNAR mechanism for missing data. The final decision on the use of the MI-RD vs Copy-Reference for this endpoint will be done at the time of the analysis and reported in the CSR.

Whether for MI-RD or Copy-Reference approach, the adjusted estimated treatment differences in means for global SANDE score between cenegeerin and vehicle at week 12 will be displayed together with the corresponding two-side 95% confidence intervals and p-value.

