12.2 SANDE derivation

The SANDE questionnaire is comprised of two questions:

- How often do your eyes feel dry and/or irritated?
- How severe you feel your symptoms of dryness and/or irritation are?

This questionnaire uses a 100 mm horizontal line for each question to assess ocular discomfort and/or dryness experienced by the patients. In the SANDE questionnaire, frequency of symptoms ranges from “rarely” to “all of the time” and the severity of symptoms ranges from “very mild” to “very severe”. Patients are asked to place a mark on the two given lines based on the extent of their symptoms.

The locations of the marks made by the patients on the 100 mm horizontal lines will be measured in mm from left to right and recorded as frequency and severity score, respectively.

The global SANDE score will be calculated by multiplying the frequency score by the severity score and obtaining the square root.

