15.5 SAS Code for the primary analysis

15.5.1 Schirmer I test >10mm/5min at week 4

Standard	Alternative code in case of no convergence
<pre> PROC MI DATA= EFFICACY01 NIMPUTE=200 SEED=820520 OUT=EFFICACY_MONO1; VAR BASVAL SCHIRMER_W2 AVAL; MCMC CHAIN=SINGLE NBITER=200 NITER=100 IMPUTE=MONOTONE; WHERE TRT=1; RUN; PROC MI DATA=EFFICACY01 NIMPUTE=200 SEED=820520 OUT=EFFICACY_MONO2; VAR BASVAL SCHIRMER_W2 AVAL; MCMC CHAIN=SINGLE NBITER=200 NITER=100 IMPUTE=MONOTONE; WHERE TRT=2; RUN; DATA EFFICACY_MONO; SET EFFICACY_MONO1 EFFICACY_MONO2; RUN; </pre>	<pre> PROC MI DATA= EFFICACY01 NIMPUTE=200 SEED=820520 OUT=EFFICACY_MONO; VAR BASVAL TRT SCHIRMER_W2 AVAL; MCMC CHAIN=SINGLE NBITER=200 NITER=100 IMPUTE=MONOTONE; RUN; </pre>
<pre> PROC SORT; BY _IMPUTATION_ SUBJID; RUN; </pre>	
<pre> PROC MI DATA=EFFICACY_MONO SEED=200582 NIMPUTE=1 OUT=EFFICACY_IMP; BY _IMPUTATION_; CLASS TRT AGE SEX EOTSTT; MONOTONE REG(AVAL = TRT AGE SEX BASVAL / DETAILS); MNAR MODEL(AVAL / MODELOBS= (EOTSTT='NOT COMPLETED')); VAR TRT AGE SEX BASVAL SCHIRMER_W2 AVAL; RUN; </pre>	<pre> PROC MI DATA=EFFICACY_MONO SEED=200582 NIMPUTE=1 OUT=EFFICACY_IMP; BY _IMPUTATION_; CLASS TRT AGE SEX EOTSTT; MONOTONE REG(AVAL = TRT AGE SEX BASVAL / DETAILS); MNAR MODEL(AVAL / MODELOBS= (TRT=2 /*Vehicle*/)); VAR TRT AGE SEX BASVAL SCHIRMER_W2 AVAL; RUN; </pre>

Standard	Alternative code in case of no convergence
<pre> DATA EFFICACY_IMP; SET EFFICACY_IMP; IF AVAL>10 THEN AVALC='Y'; ELSE AVALC='N'; RUN; ODS OUTPUT DIFFS=GLIMMIX_DIFFS; ODS OUTPUT PARAMETERESTIMATES=ESTIMATES; PROC GLIMMIX DATA=EFFICACY_IMP METHOD = QUAD; BY _IMPUTATION_; CLASS TRT(REF="1") AGE(REF="<=XX") SEX(REF="F") SITEID; MODEL AVALC(EVENT='Y')=TRT AGE SEX BASVAL /S DIST=BINARY LINK=LOGIT OR; RANDOM INTERCEPT / SUBJECT=SITEID; LSMEANS TRT / ILINK ODDSRATIO CL DIFF; RUN; ODS OUTPUT PARAMETERESTIMATES=POOLED_ESTIMATES; PROC MIANALYZE PARMS = ESTIMATES ; CLASS TRT AGE SEX; MODELEFFECTS INTERCEPT TRT AGE SEX BASVAL ; RUN; ODS OUTPUT PARAMETERESTIMATES=POOLED_DIFFS; PROC MIANALYZE DATA = GLIMMIX_DIFFS ; MODELEFFECTS ESTIMATE; STDERR STDERR; RUN; DATA POOLED_ODDS_RATIO; SET POOLED_DIFFS; ODDSRATIO=EXP(ESTIMATE); ODDS_95LL=EXP(LCLMEAN); ODDS_95UL=EXP(UCLMEAN); RUN; </pre>	

15.5.2 Change from baseline in the global SANDE score at week 12

Standard	Alternative code in case of no convergence

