<pre> PROC MI DATA= EFFICACY01 NIMPUTE=200 SEED=37103939 OUT=EFFICACY_MONO1; VAR BASVAL SANDE_W2 SANDE_W4 SANDE_W8 AVAL; MCMC CHAIN=SINGLE NBITER=200 NITER=100 IMPUTE=MONOTONE; WHERE TRT=1; RUN; PROC MI DATA=EFFICACY01 NIMPUTE=200 SEED=37103939 OUT=EFFICACY_MONO2; VAR BASVAL SANDE_W2 SANDE_W4 SANDE_W8 AVAL; MCMC CHAIN=SINGLE NBITER=200 NITER=100 IMPUTE=MONOTONE; WHERE TRT=2; RUN; DATA EFFICACY_MONO; SET EFFICACY_MONO1 EFFICACY_MONO2; RUN; </pre>	<pre> PROC MI DATA= EFFICACY01 NIMPUTE=200 SEED=37103939 OUT=EFFICACY_MONO; VAR BASVAL TRT SANDE_W2 SANDE_W4 SANDE_W8 AVAL; MCMC CHAIN=SINGLE NBITER=200 NITER=100 IMPUTE=MONOTONE; RUN; </pre>
<pre> PROC SORT; BY _IMPUTATION_ SUBJID; RUN; </pre>	
<pre> PROC MI DATA=EFFICACY_MONO SEED=200582 NIMPUTE=1 OUT=EFFICACY_IMP; BY _IMPUTATION_; CLASS TRT AGE SEX EOTSTT; MONOTONE REG(AVAL = TRT AGE SEX / DETAILS); MNAR MODEL(AVAL / MODELOBS= (EOTSTT='NOT COMPLETED')); VAR TRT AGE SEX BASVAL SANDE_W2 SANDE_W4 SANDE_W8 AVAL; RUN; </pre>	<pre> PROC MI DATA=EFFICACY_MONO SEED=200582 NIMPUTE=1 OUT=EFFICACY_IMP; BY _IMPUTATION_; CLASS TRT AGE SEX EOTSTT; MONOTONE REG(AVAL = TRT AGE SEX / DETAILS); MNAR MODEL(AVAL / MODELOBS= (TRT=2 /*Vehicle*/)); VAR TRT AGE SEX BASVAL SANDE_W2 SANDE_W4 SANDE_W8 AVAL; RUN; </pre>

Standard	Alternative code in case of no convergence
<pre>ODS OUTPUT DIFFS=DIFFS; ODS OUTPUT PARAMETERESTIMATES=ESTIMATES; PROC MIXED DATA=EFFICACY_IMP; BY _IMPUTATION_; CLASS TRT(REF="1") SEXC(REF="F") SITEID; MODEL AVAL=TRT AGE SEXC BASVAL /S; RANDOM INTERCEPT / SUBJECT=SITEID; LSMEANS TRT / CL DIFF; RUN; ODS OUTPUT PARAMETERESTIMATES=POOLED_ESTIMATES; PROC MIANALYZE PARMS = ESTIMATES ; CLASS TRT SEXC; MODELEFFECTS INTERCEPT TRT AGE SEXC BASVAL ; RUN; ODS OUTPUT PARAMETERESTIMATES=POOLED_DIFFS; PROC MIANALYZE DATA = DIFFS ; MODELEFFECTS ESTIMATE; STDERR STDERR; RUN;</pre>

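### The switch from MI-RD to Copy Reference for SANDE rests on an undefined 'convergence' test, judged after unblinding, with no minimum number of retrieved dropouts

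*SAP*

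**What the plan says.** SAP 10.1.2 imputes monotone-missing values by a regression informed only by retrieved dropouts, that is, patients who stopped treatment but have the endpoint measured (called donors below). For SANDE, the rule for leaving this method is: "If there are not enough retrieved dropouts for convergence of MI-RD regression model, a Copy Reference approach will be adopted". On timing, the SAP says: "The final decision on the use of the MI-RD vs Copy-Reference for this endpoint will be done at the time of the analysis". The Schirmer endpoint has the same trigger: "If there are not enough retrieved dropouts for convergence of MI-RD regression model, a reference-based Multiple Imputation (MI) approach will be adopted". Protocol 9.4.3.1 carries the same rule and timing and allows different approaches for the two co-primary endpoints. SAP 6.2 places the analyses after the database is locked and unblinded.

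The SANDE donor model is given in two forms.

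- **SAP 10.1.2.2 (text):** a regression "including the baseline global SANDE score, gender, age class, and intermediate global SANDE scores up to week 12". The opening of 10.1.2 adds treatment arm.
- **SAP 15.5.2 (code):** "MONOTONE REG(AVAL = TRT AGE SEX / DETAILS", so arm, age class and sex only.

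The code column that holds Copy Reference is headed "Alternative code in case of no convergence". Neither text nor code restricts the imputed scores. By SAP 12.2 the global score cannot leave 0–100: "This questionnaire uses a 100 mm horizontal line for each question", and the score comes from "multiplying the frequency score by the severity score and obtaining the square root".

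**The concern.** Convergence is a property of iterative fitting. The donor step is an ordinary linear regression with a closed-form solution. It can be fitted as soon as donors outnumber coefficients and the design is full rank. The stated trigger therefore need not fire when the donors carry almost no information.

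Two readings follow, and they are alternatives.

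- **Literal:** MI-RD is kept whenever it can be fitted. With a handful of donors, the pooled standard error of the SANDE comparison can become very large. Both co-primary endpoints must succeed, so the trial could fail for this reason alone.
- **Judgement:** the final-decision wording lets the analyst drop a poor fit. The method for a co-primary endpoint is then chosen with treatment codes known, in just the setting where the two methods can give different answers.

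SAP 7.5 gives subgroup pooling to the Blind Data Review Meeting (BDRM) before lock. It gives no such role for this choice.

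**Working it through.** **1. The plan's own figure.** SAP 5 gives a difference of 15, SD 20, 45 evaluable per arm and one-sided alpha 0.025. SE = 20 × √(2/45) = 4.22, and 15/4.22 = 3.56. The noncentral t distribution gives 94.0%, as stated. With 95.8% for Schirmer, 0.958 × 0.940 = 0.90, which matches the overall power.

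**2. Donors needed for a fit.**

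- Code model: intercept, arm, age class, sex = 4 coefficients. One residual df needs 5 donors.
- Text model: those 4 plus baseline and weeks 2, 4 and 8 = 8 coefficients. One residual df needs 9 donors.

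**3. Why few residual df hurt.** Each imputation draws the residual variance as SSE/χ² on ν residual df. Relative to SSE/ν, the mean of that draw is ν/(ν − 2). This is infinite at ν = 1 or 2, equals 4/2 = 2 at ν = 4, and 8/6 = 1.33 at ν = 8.

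**4. Simulated power.** These inputs are assumed, because the documents do not give them: 50 patients per arm; week 12 missing in 5 per arm (the 10% in SAP 5); baseline mean 65; between-visit correlation 0.6; donors drawn at random; the full 15-point effect in everyone. Each trial used 200 imputations, ANCOVA without the site effect, and Rubin's rules. The main runs had 600 to 1,000 trials per setting. Ranges cover repeat runs with slightly different assumptions.

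| Residual df | Donors, code model | Power | Donors, text model | Power |
|---|---|---|---|---|
| 1 | 5 | 6–9% | 9 | 6–8% |
| 2 | 6 | 35–41% | 10 | 35–42% |
| 4 | 8 | 74–80% | 12 | 80–81% |
| 8 | 12 | 88–91% | 16 | 92–94% |

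The median pooled SE at 1 df is roughly 50 (code) or 53–62 (text). At 8 df it is 4.6–4.8 or 4.4. Copy Reference gives 88–94% (code covariates) and 96–97% (text covariates). It was run without an arm term, whereas the code keeps TRT in the model while fitting vehicle patients only.

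**5. Sensitivity to the assumptions.**

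- With 2 missing per arm, power at 1, 2 and 4 df is about 13–16%, 65–68% and 88–93%.
- With correlation 0.4 or 0.75, code-model power at 2 df is 51% or 29%.
- Averaging over donor numbers at assumed retrieved-dropout rates of 3–15% (5 missing per arm, 30% male), the literal rule gives 74–90% (code) and 72–97% (text).

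**6. How often the choice matters.** With 5 missing per arm and a true effect, MI-RD and Copy Reference disagree on significance in 85, 56, 20 and 7% of trials (code) and 90, 57, 16 and 4% (text) at 1, 2, 4 and 8 df.

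**7. Type I error, nominal 2.5%.** MI-RD gives 0.1–1.3%, Copy Reference 1.1–2.0%, and taking the smaller p-value 1.5–2.4% (Monte Carlo SE 0.25 points).

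**8. Effect of a 0–100 limit.** Redrawing out-of-range values brings power at 1–2 df back to roughly 90%. Most of that comes from the scale. With 5 donors, limited MI-RD gave 91% (SE 4.40), while ignoring the donors and imputing uniform noise on 0–100 gave 89% (SE 4.43). The limited arm means were 44.1 and 52.4 against true means of 40.3 and 54.8, so a gap of 14.5 shrank to 8.3.

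**The case against.** The strongest reply is that no one has to keep a 1-df fit. Both documents speak of having enough retrieved dropouts and leave a final decision, so a sensible statistician would switch. The code-column heading is weak evidence for the literal reading, because it also covers the pooled-arm MCMC fallback, where convergence is a real criterion. This stands, and it means the power collapse and the unblinded choice cannot both apply. It does not remove the point, because each reading leaves a defect that one written number would close.

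The frequency is also unknown. The documents give no expected number of retrieved dropouts, and treatment lasts only four weeks. The text-model collapse needs 9 or 10 donors in addition to the missing patients. This stands too.

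The literal rule is conservative for type I error, and the MAR, tipping-point, complete-case and per-protocol analyses in SAP 10.1.3 and 10.1.4 would show the dependence. That is true, but they would not change the primary test. The Pre-Analysis Review document named in SAP 7.10 may already settle the choice on masked data; it was not available to check.

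A reader might infer that the missing 0–100 limit is the main defect and that adding it is enough. Step 8 does not support this. At 1–2 residual df the limit mostly hides the lack of donor information and pulls imputed means towards mid-scale. Nor is it neutral: with treated discontinuers made about 25 points worse, limited 1-df imputation gave a treated mean of 58.8 against a true 65.1.

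**Conclusion.** The concern holds as a gap in pre-specification. The only written trigger is one that a closed-form regression need not fail, no minimum is stated, the text and code donor models differ, and the choice falls after unblinding.

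Under the literal reading, with 5 missing per arm, SANDE power is about 6–9% at 1 residual df, 35–42% at 2, 74–81% at 4 and 88–94% at 8, against 94.0% planned. The loss is small from about 8 residual df. Under the judgement reading, the cost is an unblinded choice between methods that can disagree.

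A reader might go further and infer that this trial will lose its power or that its type I error is inflated. The documents support neither. The number of retrieved dropouts and of missing patients is not given, and no inflation was found even when the smaller p-value was taken. The Schirmer effect is modest: 87% (code, 6 donors) or 91% (text, 7 donors) at 1 df, against 95–96%. This is a cheap improvement to the plan. It does not show that the primary analysis is invalid.

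**What to change.** 1. In SAP 10.1.2, replace 'convergence' by a number. For example: use MI-RD only if the donor regression is full rank with at least 8 residual df (12 donors under the code model, 16 under the text model), otherwise Copy Reference. The sponsor may set another stated floor. Without a scale limit, power at exactly 4 residual df is 74–81%.
2. Apply and record the rule per endpoint on masked data at the BDRM before lock, and remove the wording that leaves the decision to the analysis. The independent statistician can confirm that both arms have donors without giving the split. List the change in SAP 7.9, because protocol 9.4.3.1 carries the same rule. If the Pre-Analysis Review document already does this, cite it in 10.1.2.
3. State one SANDE donor model and make 10.1.2.2 and 15.5.2 agree.
4. Let the tipping point in SAP 10.1.3, now worded for MI-RD only, follow the method used. Protocol 9.4.3.2 already allows the wash-out base.

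Restricting imputed SANDE scores to 0–100 is a secondary option or a sensitivity analysis. It does not replace the floor. The key secondary endpoints in SAP 10.2.2.4 to 10.2.2.6 use the same trigger and could take the same rule; its effect there was not calculated.

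The cost is SAP text and code, with no new data or patients. The downside is that MI-RD, which the estimand in SAP 7.3 relies on, is used less often. At an assumed 10% retrieved-dropout rate (5 missing per arm, 30% male), MI-RD is used in 89% (code) or 65% (text) of trials under the literal rule, 75% or 31% with a 4-df floor, and 30% or 5% with an 8-df floor.
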